At the Albert Einstein College of Medicine-Montefiore Hidradenitis Suppurativa Center (HSC), high-dose intralesional triamcinolone (20-40 mg/mL) is consistently used for hundreds of patients with inflammatory lesions. In an earlier retrospective review, it was reported that patients receiving high-dose intralesional triamcinolone (ILTAC) experienced improvement of disease state, quality of life, and overall satisfaction. Additionally, the majority of patients were interested in receiving future ILTAC injections as clinically indicated. Given the immense disease burden of HS, optimizing ILTAC dosing may dramatically improve medical management and quality of life (QOL) for our patients. We are seeking to determine optimal dosing by comparing response parameters of low dose (10 mg/mL) versus two concentrations of high-dose (20mg/mL and 40 mg/mL) triamcinolone injections in HS patients with active inflammatory lesions.

Due to the complex pathophysiology of HS, treatment poses a formidable challenge, incorporating antibiotics, anti-androgens and anti-inflammatory drugs. The latter includes systemic biologics and local corticosteroid injections. The standard corticosteroid used for acute nodules, abscesses, and draining sinus tracts reduces pain, redness, and swelling in 12- to

24-hours. Although ILTAC is considered a standard of care for acute flares in HS, studies documenting efficacy and side effect profile at varying doses are remarkably sparse.

Fajgenbaum et al. performed a double-blinded, randomized, placebo controlled trial comparing normal saline (NS), intralesional TAC 10 mg/mL (ILTAC-10), and intralesional TAC 40 mg/mL (ILTAC-40). There were no statistically significant differences between the varying concentrations and normal saline. However, the study was seriously under powered given the subject and lesion randomization parameters. Another major flaw in the study design was the randomization of lesions as opposed to participants. With this approach, systemic effects of the injection were not taken into account and likely obscured interpretation of the results.

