## 2.0 STUDY DESIGN

### a) Study Design

[figure not shown]
A double-blinded, randomized, placebo-controlled study examining the relative efficacy of ILTAC-10, ILTAC-20, and ILTAC-40 versus placebo for acute flares of HS in subjects with moderate to severe HS.

The duration of the study will be approximately 4 weeks for each enrolled patient and will include an initial screening/randomization/treatment visit and a 4-week follow-up period.

During the initial visit, subjects who meet the study's eligibility criteria will be randomized to receive either ILTAC-10, ILTAC-20, ILTAC-40, or normal saline (NS) placebo in a 1:1:1:1 ratio. The volume of ILTAC or NS administered is calculated based on the largest dimension of the HS lesion, which is measured by its greatest width in mm. For example, if a lesion is irregular in shape, measuring 22mm by 18mm, 22mm will be the largest dimension used for calculating volume. The administered volume (ml) is scaled by increments of 0.2ml, which corresponds to the HS lesion size, and ranges from 0.2ml to 2.0ml. The maximum volume of either ILTAC-10, ILTAC-20, ILTAC-40 or NS administered to any given HS lesion is 2.0ml.

**Figure 1.** Hidradenitis Suppurativa Lesion Size and Volume of administration of ILTAC-10, ILTAC-20, ILTAC-40, or normal saline placebo.

| HS lesion size (cm) | Volume (ml) |
|---------------------|-------------|
| 0.0 – 0.49          | 0.2         |
| 0.5 – 0.99          | 0.4         |
| 1.0 – 1.49          | 0.6         |
| 1.5 – 1.99          | 0.8         |
| 2.0 – 2.49          | 1.0         |
| 2.5 – 2.99          | 1.2         |
| 3.0 – 3.49          | 1.4         |
| 3.5 – 3.99          | 1.6         |
| 4.0 – 4.49          | 1.8         |
| 4.5 – 5.0           | 2.0         |

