### Hypothesis

Given the generally accepted anti-inflammatory property of fluorinated corticosteroids, it is anticipated that treatment with ILTAC will be superior to normal

saline for both acute HS flares, as well as patient reported outcome measures including HS-related pain and satisfaction after treatment. Additionally we expect a dose-dependent response when ILTAC-40 is compared to ILTAC-20 and ILTAC-10. Our preliminary findings suggest there will be no difference in subject side effect profile between the ILTAC and normal saline treatment arms.

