##### *Secondary Outcomes*

- Change from baseline in NRS pain scale at days 2, 6, and 14.
- Difference in change from baseline in NRS pain scale at days 2, 6, 14, and 28 between ILTAC-10, ILTAC-20, ILTAC-40.
- Change from baseline in HS-PGA score at week 2 and 4.
- Difference in change from baseline in HS-PGA score at week 2 and 4 between ILTAC-10, ILTAC-20, ILTAC-40.
- Change from baseline in objective markers of inflammation (c-reactive protein [CRP], erythrocyte sedimentation rate [ESR], and interleukin-6 [IL-6]) at week 2 and 4.

- Change from baseline in subjective markers of inflammation (erythema, edema, and suppuration) at week 2 and 4.
- Change from baseline in lesion size at week 2 and 4.
- Difference in change from baseline in lesion size at week 2 and 4 between ILTAC-10, ILTAC-20, ILTAC-40.
- Change from baseline in Patient-Reported Outcomes Measurement Information System (PROMIS) measure of physical functioning at days 2, 6, 14, and 28.
- Difference in change from baseline in PROMIS at days 2, 6, 14, and 28 between ILTAC-10, ILTAC-20, ILTAC-40.
- Proportion of subjects reporting side effects at days 2, 6, 14, and 28.
- Difference in proportion of subjects reporting side effects at days 2, 6, 14, and 28 between ILTAC-10, ILTAC-20, ILTAC-40.
- Baseline patient satisfaction.
- Change from baseline in patient satisfaction at days 2, 6, 14, and 28.
- Serum cortisol and ACTH levels at week 2 and 4.
- Change in serum cortisol and ACTH levels from week 2 to 4.

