## 7.0 DATA ANALYSIS

- a) Statistical Methods  
We will analyze the data from the study using an intention to treat approach. Categorical variables, including presence of side effects, drainage, and physical function, will be analyzed with chi square tests. Continuous variables, such as NRS pain scale, markers of inflammation, and lesion size, will be analyzed by T-test. Sensitivity analyses or exploratory analyses may be performed to examine the effect difference for race or gender. In the unlikely case patients do not receive the treatment they will still be randomized for analysis using a per protocol approach. All statistical tests will be 2-sided, with  $p < 0.05$  considered significant.
- b) There will be no interim analysis or early stopping of the study.
- c) Confounding and effect modification will be addressed by randomization of the subjects and blinding of both the investigators and the participants.
- d) If subjects are lost to follow up, they will be analyzed in the group to which they were initially randomized.

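### The dose-versus-dose comparisons that serve the optimal-dosing purpose are unranked secondary tests, each significant at p < 0.05, so a false dose difference arises far more often than 5% of the time

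*Combined protocol and SAP*

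**What the plan says.** Section 7.0 a) gives the significance rule: "All statistical tests will be 2-sided, with $p < 0.05$ considered significant". It names two tests: "Continuous variables, such as NRS pain scale, markers of inflammation, and lesion size, will be analyzed by T-test" and "Categorical variables, including presence of side effects, drainage, and physical function, will be analyzed with chi square tests". The word exploratory occurs once there, for subgroups: "Sensitivity analyses or exploratory analyses may be performed to examine the effect difference for race or gender".

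Section 2.0 names one primary outcome, the week-4 change in NRS pain, followed by a long list of secondary outcomes. Five of these compare the concentrations with each other. The first reads "Difference in change from baseline in NRS pain scale at days 2, 6, 14, and 28 between ILTAC-10, ILTAC-20, ILTAC-40". The others do the same for HS-PGA and lesion size (two visits each) and for PROMIS and side effects (four time points each). None is ranked, and none is made conditional on the primary.

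The dose question is prominent elsewhere. Section 1.0 says "We are seeking to determine optimal dosing by comparing response parameters of low dose", and the Hypothesis in Section 2.0 says "Additionally we expect a dose-dependent response when ILTAC-40 is compared to ILTAC-20 and ILTAC-10". The sample size in Section 3.0 b) covers only saline versus ILTAC-10.

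**The concern.** Leaving secondary outcomes unadjusted is common and often harmless, because the primary carries the conclusion. Here the primary does not carry the dose conclusion. Which concentration works best is answered only by the secondary comparisons, and the plan does not say which scale or which day decides it. Under the rule as written, any one of 36 efficacy comparisons between concentrations can be reported as a significant dose difference. A finding that favours a higher steroid concentration could then be chance on one scale at one visit, and the plan would give no ground for discounting it.

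**Working it through.** **Inputs from the documents.** Four arms, 1:1:1:1 (2.0 a); at least 30 per arm (3.0 b); two-sided 0.05 for every test and t-tests for continuous outcomes (7.0 a); the between-dose outcomes and their time points (2.0, Secondary Outcomes).

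**Assumed.** Pairwise tests, normal data, and a correlation of 0.2, 0.5 or 0.8 between all outcome-by-time variables. Section 3.0 b) gives 0.1 to 0.9 for one patient's pain scores over time; nothing is given between outcomes.

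**1. The plan's own figure.** SD of change = √(2 − 2ρ) = √(2 − 0.2) = 1.342 at ρ = 0.1. Two-sample t-test power (noncentral t, 58 df, difference 1, 30 per arm) = 0.81021, as printed in Table 1. The other eight rows also reproduce. This power is for one comparison at 0.05.

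**2. Count of between-dose efficacy tests.** Three concentrations give 3 pairs.

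| Outcome | Times | Tests |
|---|---|---|
| NRS pain | 4 | 12 |
| HS-PGA | 2 | 6 |
| Lesion size | 2 | 6 |
| PROMIS | 4 | 12 |
| Total | 12 | 36 |

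Without PROMIS, 36 − 12 = 24. Side effects are not counted.

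**3. Error if all tests were independent.** 1 − 0.95^k gives 14.3% for k = 3, 46.0% for 12, 70.8% for 24 and 84.2% for 36. These overstate the risk, because pairs share arms and outcomes are correlated.

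**4. Simulated error.** Three equal dose arms of 30, two-sided 5% t-tests, chance of at least one rejection:

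| Family | ρ = 0.2 | ρ = 0.5 | ρ = 0.8 |
|---|---|---|---|
| NRS, day 28 only (3 tests) | 12% | 12% | 13% |
| NRS, four times (12) | 40% | 34% | 25% |
| NRS, HS-PGA, lesion size (24) | 62% | 52% | 34% |
| All four scales (36) | 76% | 61% | 40% |

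Repeat runs agree within about two percentage points. With separate correlations between outcomes (0 to 0.9) and between times (0.1 to 0.9), the 36-test figure runs from 79% to 33%. Expected false positives among 36 tests are 36 × 0.05 = 1.8, whatever the correlation.

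**5. Does a gated sequence hold 5%?** Test ILTAC-40 versus ILTAC-10 first. Test the two adjacent pairs, each at 0.05, only if the first is significant.
- If all three means are equal, any false claim requires the first test to err: 5%.
- If ILTAC-40 and ILTAC-10 are equal but ILTAC-20 differs, only the first null is true: 5%.
- If ILTAC-40 and ILTAC-10 differ, ILTAC-20 can equal at most one of them, so at most one remaining null is true: 5%.

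**6. Power of the first step.** The documents give no difference between doses. For an assumed 0.5 points, the same formula at 30 per arm gives 29% with SD 1.342 and 48% with SD 1.0 (Table 1 at ρ = 0.5).

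**The case against.** **The dose comparisons are not confirmatory.** The formal aims on efficacy and satisfaction compare the doses with placebo, the optimal-dosing sentence is in the background, and the hypothesis states an expectation without a decision rule. This is fair: the plan nowhere calls these tests confirmatory. But it does not call them exploratory either, and 7.0 a) makes each one capable of being significant. The gap is that their status is left open. Nor is the plan without any ordering, since one primary outcome is separated from the rest; what is missing is order within the secondary outcomes.

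**The counts are a construction.** Section 7.0 a) sends physical function to chi-square, which could be one multi-group test per time point, and names no test for HS-PGA. This stands, and is why the 24-test figures are shown. The smallest case, three pairs on one scale on one day, needs no such construction and already gives about 12%.

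**Stronger readings a reader might infer.** One could add the secondary comparisons with saline (27 outcome-by-time variables × 3 = 81) to reach 117 tests, and quote about a 90% chance of a false positive with about 5.9 expected. Those figures require saline to equal every dose. If the doses are equal to each other but beat saline, as the Hypothesis anticipates for ILTAC against saline, rejections against saline are not false, and only the between-dose figures apply. One could also infer that a false dose claim is simply likely. Across the assumed range, more likely than not holds only for scales pooled together at low to moderate correlation; it does not hold for pain alone.

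**Conclusion.** The concern holds in a limited form. One unadjusted rule governs every test, and the dose question rests on unranked secondary comparisons. If the concentrations do not differ, the chance of at least one false dose difference is about 12% for day-28 pain, about 25-40% over the pain time points, and about 40-76% over 36 efficacy tests (34-62% over 24 without PROMIS), against a nominal 5%. This assumes 30 analysed per arm, pairwise t-tests and the stated correlation range. The correlation changes the size of the excess and not its presence. The claim is confined to comparisons between doses; it says nothing about the overall error when saline is included.

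**What to change.** In 7.0 a), limit claims of significance to the primary analysis and one pre-specified between-dose sequence on the day-28 change in NRS pain: ILTAC-40 versus ILTAC-10 at two-sided 0.05; then, only if that is significant, ILTAC-40 versus ILTAC-20 and ILTAC-20 versus ILTAC-10, each at 0.05. Label every other secondary outcome in 2.0 exploratory, reported as estimates with 95% confidence intervals and without significance claims.

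If the sequence is also to depend on the primary, the plan must define when the primary is met across its three dose-versus-saline tests. If any one of the three at 0.05 suffices, that gate opens by chance about 12% of the time when no arm differs.

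The cost is a few sentences, with no new data or patients, made before unblinding. Early time points and other scales could no longer be claimed as significant. The adjacent comparisons would hang on the first, so the gate may stay shut if ILTAC-20 does best, and power for the first step is modest if the dose difference is small (step 6). By comparison, Bonferroni over the three pairs would cut power from 81.0% to 66.3% at a difference of 1 and SD 1.342, and would need 40 per arm for 80%; using a difference of 1 between doses is itself an assumption.

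A simpler and acceptable alternative is to label all between-dose comparisons exploratory.

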#### Outcomes

##### *Primary Outcome*

- Change from baseline in NRS pain scale at week 4 (Appendix B).

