| HS-PGA   | X          |       |       | X      | X      |
| Treatment: NS,
ILTAC-10,
ILTAC-20 or
ILTAC-40 | X          |       |       |        |        |
| Patient
Satisfaction
Survey                      | X          | X     | X     | X      | X      |
| PROMIS
Survey                                       | X          | X     | X     | X      | X      |
| NRS Pain Scale   | X          | X     | X     | X      | X      |
| Side Effect
Assessment                              |            | X     | X     | X      | X      |

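### Section 7.0 keeps lost patients in their arm but gives no value for a missing week-4 NRS score, and the unadjusted t-test it names uses neither baseline adjustment nor the earlier NRS scores

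*Combined protocol and SAP*

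**What the plan says.** The primary outcome in Section 2.0 is "Change from baseline in NRS pain scale at week 4". Section 7.0 a) names one method for it: "Continuous variables, such as NRS pain scale, markers of inflammation, and lesion size, will be analyzed by T-test". It mentions no covariate, model or imputation.

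On who is analysed, Section 7.0 a) states "We will analyze the data from the study using an intention to treat approach". The same paragraph adds "In the unlikely case patients do not receive the treatment they will still be randomized for analysis using a per protocol approach". The per-protocol set is not defined, and nothing says whether that analysis is primary or supplementary. Section 7.0 d) adds "If subjects are lost to follow up, they will be analyzed in the group to which they were initially randomized".

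The only sensitivity work named is optional and does not concern missing data: "Sensitivity analyses or exploratory analyses may be performed to examine the effect difference for race or gender".

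Earlier pain scores are planned. The secondary outcomes include "Change from baseline in NRS pain scale at days 2, 6, and 14", and the row "NRS Pain Scale" of the Section 5.0 f) calendar is marked at enrolment, days 2 and 6, and weeks 2 and 4.

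**The concern.** Section 7.0 d) is an allocation rule, not a missing-data rule. A patient kept in an arm without a week-4 score has no change to enter into a t-test. With no substitute value named, the test runs on the remaining patients. An analyst who took the promise to analyse everyone literally would have to invent a value. Both could claim to follow Section 7.0 and yet report different primary results.

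If patients stay or leave because of how their pain responded, those who remain in an arm no longer represent everyone randomised to it. The estimate shrinks if saline loses its worst responders and grows if an active arm does. The plan collects pain scores that could reduce this bias, but the named test does not use them.

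The per-protocol sentence raises a smaller question of the same kind: whether a randomised but untreated patient is in the primary test.

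**Working it through.** **Inputs from the plan.** Section 3.0 b) and Table 1: difference 1; SD 1 at both time points (the text ties this to baseline and day 2); correlation rho from 0.1 to 0.9; two-sided alpha 0.05; 30 per arm from the rho 0.1 row.

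**The plan's own figure.** SD of change = sqrt(1 + 1 − 2 × 0.1) = 1.342. Noncentral-t power with 30 per arm is 0.8102, matching Table 1 (0.81021). It counts 30 patients per arm with both scores.

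**Assumptions of this review.** SD 1 also holds at week 4. All visits are equally correlated. The true effect is 1.00 at every visit after baseline. One arm loses its worst 10% or 20% (3 or 6 of 30) at week 4 and the other loses nobody. The documents give no dropout rate.

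**Closed form when loss follows day-14 change.** The covariance of day-14 change and week-4 change is rho − rho − rho + 1 = 1 − rho, and each variance is 2(1 − rho), so their correlation is 0.5. Losing the worst share p shifts that arm's mean by 0.5 × SD of change × phi(z)/(1 − p), where z is the standard normal quantile at 1 − p and phi its density:

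- p = 0.10: 0.5 × 1.342 × 0.1755/0.90 = 0.131
- p = 0.20: 0.5 × 1.342 × 0.2800/0.80 = 0.235

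The shift is proportional to the SD: 0.196/0.352 at SD 1.5 and 0.262/0.470 at SD 2.

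**Simulation** (30 per arm, 6000 runs, Monte Carlo SE 0.005 or less; true effect 1.00). Each cell gives 10% loss / 20% loss.

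| Loss driven by | rho | Arm losing | t-test on available changes | Baseline-adjusted | Baseline plus days 2, 6, 14 |
|---|---|---|---|---|---|
| Day-14 change | 0.1 | saline | 0.879 / 0.768 | 0.985 / 0.972 | 0.998 / 0.997 |
| Day-14 change | 0.1 | active | 1.132 / 1.230 | 1.015 / 1.025 | 1.001 / 1.001 |
| Day-14 change | 0.5 | saline | 0.911 / 0.829 | 0.956 / 0.908 | 1.004 / 0.996 |
| Day-14 change | 0.5 | active | 1.093 / 1.162 | 1.049 / 1.083 | 1.000 / 0.995 |
| Week-4 change | 0.1 | saline | 0.750 / 0.543 | 0.859 / 0.730 | 0.862 / 0.735 |
| Week-4 change | 0.1 | active | 1.242 / 1.453 | 1.142 / 1.269 | 1.139 / 1.264 |

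**Why baseline adjustment helps unevenly.** Given baseline, the correlation left between day 14 and week 4 is (rho − rho²)/(1 − rho²) = rho/(1 + rho). That is 0.1/1.1 = 0.09 at rho 0.1 and 0.5/1.5 = 0.33 at rho 0.5. At low correlation little selection remains after baseline is in the model; at 0.5 a good part does.

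**Why the last column is near 1.00 in the day-14 rows.** The scores that drive loss are in the model and observed for every lost patient, so this follows from the set-up. If day 14 is also unrecorded for the lost patients at rho 0.5, the estimate is about 0.98/0.96 (saline loses) or 1.02/1.04 (active loses).

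**Shifting missing scores.** Worsening an arm's missing scores by 1 point moves the effect by the missing share, 0.10 or 0.20. In the last row, 1.139 − 0.10 = 1.04 and 1.264 − 0.20 = 1.06. The same active-arm shift does nothing when saline is the arm losing patients; there the saline scores must be shifted: 0.862 + 0.10 = 0.96 and 0.735 + 0.20 = 0.94. At SD 2 the bias doubles, so a 1-point active-arm shift leaves 1 + 2 × 0.139 − 0.10 = 1.18 and 1 + 2 × 0.264 − 0.20 = 1.33. One fixed shift in one arm is therefore not enough.

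**The case against.** **Complete-case analysis is inferred.** Section 7.0 d) promises to analyse lost patients and 7.0 a) declares intention to treat. A reader might conclude that the plan prescribes complete-case analysis; it does not. What it leaves open is the value to use. The bias figures apply only if the t-test is run without one.

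**The scenarios are severe.** One arm losing exactly its worst responders, with no loss in the other, is an illustration and not a forecast. The trial has one treatment visit and four weeks of follow-up. The documents support neither a dropout rate nor a direction, so a reader should not infer that the trial would overstate, or understate, the drug's effect.

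**The larger model is not always needed.** At rho 0.1, the row that sets the sample size, baseline adjustment alone comes within 0.03. At rho 0.5 the error left is 0.04 to 0.09 points. This stands: baseline adjustment is the minimum, and the repeated-measures model is a preference with a gain at higher correlation. Nor does that model cure everything; if unobserved week-4 pain drives loss, it does no better than baseline adjustment.

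**Power is a separate matter.** At rho 0.1, power is 0.7965 with 29 evaluable per arm, 0.7666 with 27 and 0.7149 with 24. At rho 0.3, 24 per arm still gives 0.8176. It is tempting to conclude that the trial is underpowered, but Section 3.0 b) gives 30 as a minimum and the result depends on rho. These figures bear on the sample-size allowance, not on the missing-value rule.

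**The per-protocol sentence is minor.** The plan calls the situation unlikely, and Section 2.0 a) puts randomisation and treatment in one visit.

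**Conclusion.** The point holds as a gap in the primary analysis for which a better method is available. Section 7.0 supplies no week-4 value for a lost patient, and the named t-test makes no use of baseline adjustment or earlier NRS scores. Under the stated assumptions (SD 1, equal correlations, 10% or 20% one-sided loss on day-14 change), the t-test is off by 0.12 to 0.23 points at rho 0.1 and 0.09 to 0.17 at rho 0.5, against a planned effect of 1. Baseline adjustment cuts this to 0.03 or less at rho 0.1 and by about half at rho 0.5. With a larger SD the bias grows in proportion. If loss follows week-4 pain itself, an error of about 0.14 to 0.27 remains whichever of the two models is used, and only a sensitivity analysis can show how far the result depends on it.

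The change should be made, with medium confidence in its practical size, because the amount and pattern of loss are unknown. The per-protocol wording needs a one-line clarification and should affect few patients.

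**What to change.** In Section 7.0:

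1. Replace the week-4 t-test with a baseline-adjusted analysis of week-4 NRS in all randomised patients by assigned arm, treated or not. Preferably use a likelihood-based repeated-measures model on NRS at days 2, 6, 14 and 28, with baseline NRS, arm, visit and arm-by-visit, and take the week-4 contrast of each ILTAC arm with saline. A patient without a week-4 score then still contributes earlier scores.
2. Add a sensitivity analysis that shifts missing week-4 scores over a range of values, in each arm separately and in both directions.
3. Delete the per-protocol sentence or label that analysis supplementary and define its set.

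Before day-2 and day-6 scores enter the model, reconcile three places. The Section 5.0 f) calendar marks NRS at every time point. The phone contacts in Section 2.0 b) list the satisfaction survey, PROMIS and side effects but not NRS. Appendix D contains two 0-to-10 pain items, at rest and on touch, while Appendix B describes one scale. State which item is the NRS and that it is asked on the calls.

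No new visits are needed. The cost is wording, slightly more analysis work, and software that fits these models; Section 8.0 a) names only Excel, as an example.
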